Allergic diseases are the commonest chronic diseases of childhood in the UK, and continue to increase in prevalence worldwide at an alarming rate. Its ontogeny remains poorly understood. [name] interest in the field of developmental immunology and allergy has led to many contributions in the field of the early life origins of allergic disease (Jones et al., 2002). There is a busy tertiary paediatric allergy service at St Mary's Hospital, with a very active research base. There is considerable interest in the interactions between infectious, allergic and inflammatory diseases in early childhood.

Current major research interests in the department include the pathogenesis and characterisation of food hypersensitivity, the treatment of asthma and the primary prevention of allergic disease (McCann et al., 2007). Routine serum samples are taken from children attending the allergy clinics, and we would like to take additional samples for the characterisation of allergic immune responses and genetic and epigenetic correlates of allergic disease.

Projects with the Centre for Respiratory Infection (CRI)

This project is supported by the Centre for Respiratory Infection, based at Imperial College (including at St Mary's site). This world-class association of clinicians and scientists includes several groups working on the immunopathology of respiratory infection and allergy, and the project will capitalise on the expertise of these groups, both for enhanced diagnostic work on patient samples, and also for scientific lines of enquiry. The location of St Mary's Hospital means that it will greatly benefit from input from CRI teams, not least because many patients enrolled in the study will have respiratory infections and allergic airways disease. Below are some examples of how patients recruited will contribute to studies at the CRI.

Some babies with bronchiolitis caused by RSV (a common viral cause in babies) have a more severe course of infection than others. One possibility for this is that babies with more severe RSV illness in fact have multi-pathogen infections (see (Brunstein et al., 2008)), and collaboration with CRI labs will allow an intensive search for additional pathogens together as well as a parallel approach in which the contribution of the antiviral immune response is considered (Openshaw, 2005).

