 - To what extent is immune system function governed by non-heritable factors, such as dietary and nutritional status?

In addition to the above, we anticipate that the development of robust and systematic methods to recruit considerable numbers of children into this research programme will create

a useful pathway that would be applicable to patients presenting to St Mary's Hospital with emerging infections, such as PVL staphylococcal disease or emerging viral infections.

Inclusion Criteria

St Mary's Hospital

- Children presenting via any means to St Mary's Hospital; this would include the A&E department, the general and infectious disease wards and the paediatric intensive care unit.
- Children needing blood tests for any clinical reason (ie we will not take blood samples from children who would not otherwise be having them taken).
- Children who, in the clinical judgement of the doctor assessing them, have presented because of a condition consistent with an infectious, inflammatory or allergic process.
- We will recruit well children into this study to act as controls. These will be children who are in any case having blood tests, for instance children undergoing elective surgery

Collaborating sites

- Children needing blood tests for any clinical reason (ie we will not take blood samples from children who would not otherwise be having them taken).
- Children presenting at collaborating sites with a proven or suspected respiratory infection **or** proven or suspected infection with a pathogen associated with respiratory disease without respiratory manifestations.

Exclusion criteria

- Children must be aged 16 years or younger.
- Children re-presenting with the same condition would not be re-enrolled, but they could be re-enrolled if they have a new condition.
- If there is a concern that the requirements of the study are not fully appreciated by the parent/guardian or child due to for example a lack of comprehension of information given in English then they will be excluded.

Sample Size

We would hope to enroll 1000 patients over a 3 year period, with a range of diagnoses. The methods of gene expression and proteomic biomarker detection require groups of 30-50 patients within each diagnostic category (for instance viral infection vs. bacterial infection), in order to have adequate power for analysis.

Confirmatory studies on twice this number are required for validation.

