However, even rare presentations of disease would be of interest as individual or small groups are amenable to analysis at a molecular level.

METHOD

Enrolling patients.

When the research project is going to start, we will educate the paediatric team working at St Mary's Hospital or a collaborating site, including dedicated research nurses, about the project. We will ensure that the scientific basis for the project, the entry criteria and the consenting process are clearly understood.

If members of the paediatric team believe that a patient they are assessing qualifies to enter the study, they will be encouraged to enrol them either directly themselves, or by asking a member of the clinical research team to come and consent the child and take bloods (for

instance a research nurse or clinician scientist). The project will be explained using an age-appropriate participant information sheet.

The consenting procedure

This will involve the following. We will explain to children and their carers that there is a clinical need for a blood test, and that we would like to take a small extra volume of blood at the same time for a research project. In addition, if other samples are being collected for clinical reasons, such as urine or nasopharyngeal aspirates, if the sample volume is sufficient we will seek consent to take an aliquot for research purposes. We may seek consent to collect additional non-invasive samples for research purposes, such as urine samples or throat swabs, in some cases where there is not a clinical need to collect these.

We will recruit well children into this study to act as controls. These will be children who are in any case having blood tests, for instance children undergoing elective surgery. This will be important in order to give us a baseline comparator. Informed consent will be sought in all instances.

Blood sample collection

Sample collection will be performed either by the clinical team or research nurses, if consent is given. The normal clinical bloods will be taken along with additional research samples, with the following volumes:

Child above 5 years

Serum – 4ml, EDTA – 4ml, PAX – 2.5ml

Children below 5 years

Serum – 1ml, EDTA – 1ml, PAX – 2ml

(We recognise that these volumes will not always be obtainable in smaller children.)

Serum samples will be spun and frozen for proteomic work, such as biomarker characterisation.

EDTA samples will be frozen pending DNA extraction for genomic analysis.

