- 1) We will use state-of-the-art diagnostic techniques, which are not ordinarily available for routine use in hospital, to look for infections in blood and in other samples if they are taken, such as cerebro-spinal fluid (CSF). These tests include polymerase chain reaction (PCR).
- 2) We will look at the range of proteins that are present in the children's blood - infections or diseases may be defined by the 'signature' of proteins in the blood.
- 3) We will look at which genes are being used by the white cells in the blood to fight infection in order to understand how the body is responding. We may also be able to diagnose an illness by looking at which genes are being used by the white cells.
- 4) We will look for differences in the genes (part of the DNA) between patients which might explain why two patients behave differently - for instance, why does one child get a sore throat but another child become seriously ill with the same infection?
- 5) Under a variety of laboratory conditions, we will look at how cells from the patient are functioning from an immunological point of view; for instance we will identify which cytokines (immune messenger molecules) they are making.

Statistics and Data Analysis

Sample size: Among patients presenting with symptoms of infection there will be groups of patients with common disorders such as RSV bronchiolitis and bacterial pneumonia, however much smaller numbers of patients will present with rare but important infections such as PVL staphylococcal infection, toxic shock or Kawasaki disease.

Our enrolment procedure will enable all patients to be included in the study, and as a result, there will be large groups of patients with common disorders and small numbers of patients with rare disorders.

In this regard, a formal power calculation is not possible; however, to obtain disease-specific genetic signatures a minimum of 30-50 patients in each group are required, with validation in a larger number.

Methods of analysis: Analysis of complex immunological data, including gene expression and proteomic analysis, will be undertaken in collaboration with the department of epidemiology and biostatistics at Imperial College. [name] has on-going collaboration with [name], who is a leader in application of statistical methods to large biological datasets.

Data Retention

Data and all appropriate documentation will be stored for a minimum of 10 years after the completion of the study, including the follow-up period.

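### Well controls are a convenience group with no age steering, so comparisons of an infant-heavy category with them may partly reflect age

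*Combined protocol and SAP*

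**What the plan says.** Under Inclusion Criteria, St Mary's Hospital, the protocol states: "We will recruit well children into this study to act as controls". The consenting procedure section repeats this and gives the source and purpose: well children who already need a blood test, "for instance children undergoing elective surgery. This will be important in order to give us a baseline comparator". The inclusion criteria limit the pool further: "we will not take blood samples from children who would not otherwise be having them taken".

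The one age rule, placed under Exclusion criteria, applies to everyone: "Children must be aged 16 years or younger". Age appears in two other places. One is the research blood volumes, which have a separate line for "Children below 5 years"; the other is the age-appropriate information sheet. Neither governs who is recruited as a control.

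On the case side, Statistics and Data Analysis expects that "there will be groups of patients with common disorders such as RSV bronchiolitis and bacterial pneumonia". The section on projects with the Centre for Respiratory Infection discusses RSV bronchiolitis as an illness of babies.

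On analysis, the plan says: "Analysis of complex immunological data, including gene expression and proteomic analysis, will be undertaken in collaboration with the department of epidemiology and biostatistics". It names no model, covariate or age adjustment. It also gives no number of controls, no control-to-case ratio, and no age distribution for either group.

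**The concern.** The controls will be whichever well children happen to need blood taken. Nothing ensures that any of them are infants, although at least one expected common category is described in babies. If a marker changes with age in healthy children, a comparison of infant cases with mostly older controls mixes the effect of age with the effect of disease. Part of an apparent disease signature or mechanism could then be a signature of infancy.

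There are two separate consequences. Without adjustment, the comparison is biased. With adjustment, it loses precision, and infant cases with no infant controls contribute nothing except by extrapolating a model. The second problem is settled at recruitment, so analysts cannot fix it afterwards.

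The plan also calls for validation in larger numbers. It does not say how validation controls would be found. If they come by the same route, validation would tend to repeat the age difference rather than expose it.

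**Working it through.** **Inputs.** From the documents: 30-50 patients per diagnostic category, and twice that number for validation (Sample Size). There is no stated figure on control ages or numbers to reproduce. Everything below on age is assumed, using three bands: under 1, 1-4 and 5-16 years.

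- Infant-dominated category: cases 80/15/5%.
- Older category: cases 5/15/80%.
- Mixed categories: cases 40/30/30% or 30/30/40%.
- Unsteered controls: 10/30/60%, or 0/30/70% if no infants are found.
- Steered controls: 40/30/30%, or equal thirds.

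**Precision after age adjustment.** With equal variance and a common effect, information = sum over bands of (cases × controls)/(cases + controls). The equivalent size per group is twice that. Perfect balance at 50 v 50 gives 50.

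| 50 cases | Controls | Information by band | Equivalent size per group |
|---|---|---|---|
| Infant-dominated | 50 unsteered | 4.44 + 5.00 + 2.31 = 11.75 | 23.5 |
| Infant-dominated | 50, none under 1 | 0 + 5.00 + 2.33 = 7.33 | 14.7 |
| Infant-dominated | 50 at 40/30/30% | 13.33 + 5.00 + 2.14 = 20.48 | 41.0 |
| Infant-dominated | 160 unsteered | 11.43 + 6.49 + 2.44 = 20.35 | 40.7 |
| Infant-dominated | 200 unsteered | 13.33 + 6.67 + 2.45 = 22.45 | 44.9 |
| Infant-dominated | 200 at 40/30/30% | 26.67 + 6.67 + 2.40 = 35.73 | 71.5 |
| Infant-dominated | 200, none under 1 | 0 + 6.67 + 2.46 = 9.12 | 18.2 |
| Mixed 40/30/30% | 50 unsteered | 4.00 + 7.50 + 10.00 = 21.50 | 43.0 |
| Mixed 30/30/40% | 50 unsteered | 3.75 + 7.50 + 12.00 = 23.25 | 46.5 |
| Older | 50 unsteered | 1.67 + 5.00 + 17.14 = 23.81 | 47.6 |
| Older | 50 at 40/30/30% | 2.22 + 5.00 + 10.91 = 18.13 | 36.3 |

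Controls in equal thirds give 38.2 for both the infant-dominated and the older category.

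The figure of 23.5 corresponds to a standard error sqrt(50/23.5) = 1.46 times that of perfect balance. With no infant controls, only the 7.5 + 2.5 = 10 older cases contribute. The equivalent size therefore cannot exceed 2 × 10 = 20, however many controls are added.

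**Bias without adjustment.** Suppose a marker differs by d SD between the youngest and oldest bands, with ages 1-4 halfway. In units of d:

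- Infant-dominated case mean: 0.15 × 0.5 + 0.05 = 0.125.
- Unsteered control mean: 0.30 × 0.5 + 0.60 = 0.75.
- Control mean at 40/30/30%: 0.30 × 0.5 + 0.30 = 0.45.

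The age-only difference is therefore 0.625d unsteered and 0.325d steered. For d from 0.25 to 1 SD, that is 0.16 to 0.63 SD unsteered and 0.08 to 0.33 SD steered. Steering halves the bias, roughly, but does not remove it, so an age term is still needed.

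**Validation.** Take a marker with no disease effect, an assumed marker-age correlation r, and a case-control age gap of D SD. The chance of p < 0.05 (two-sided, unadjusted) is Φ(rD/√(2/n) − 1.96) + Φ(−rD/√(2/n) − 1.96). With r = 0.3 and D = 0.5 it is 11.7% at n = 50 per group and 18.6% at n = 100. Over r = 0.1 to 0.5 and D = 0.25 to 1.0, it runs from 5.2% to 71% at n = 50 and from 5.4% to 94% at n = 100. If the age gap persists, a larger validation sample makes the false difference more likely to be confirmed.

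**The case against.** The strongest reply is that the large loss is built from assumptions. The 80/15/5% split is invented, and 23.5 also requires as many controls as cases. A single control group shared across categories could be much larger, and 160 unsteered controls come close to what steering achieves with 50 (40.7 v 41.0). For mixed categories the loss is small, and for older categories steering makes matters worse. All of this stands. It limits the point to infant-heavy categories. It does not answer the case with no infant controls, where extra numbers bring almost nothing.

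The link to the documents is also narrow. RSV bronchiolitis is the only category cited here as young. The question the protocol raises about it, why some babies are more severely ill than others, compares cases with cases. No specific RSV v well-control test is written down. That too stands, but the plan does assign well controls the general role of baseline.

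The Surplus samples section says the children need not represent the clinical range of disease. That concerns the spread of patients, not whether controls are comparable with cases. The clinical dataset mentioned there might allow adjustment, but its contents are not listed and adjustment is not promised.

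A reader might draw four stronger conclusions that the documents do not support:

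- **That the control comparisons are in fact confounded by age.** No age distribution is given, so neither the existence nor the direction of an imbalance is known.
- **That all results are affected.** Viral v bacterial contrasts do not use well controls (although age handling is not stated there either), and the question of which organisms cause illness does not depend on them. Comparisons of inherited DNA are outside the harm described here.
- **That control contrasts must be confined to one site.** The inclusion criteria already list well controls only under St Mary's. Whether to set aside cases from other sites is a separate trade-off.
- **That age is already recorded well enough.** A blood-volume split at 5 years does not show that infants can be distinguished from children aged 1-4.

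**Conclusion.** The concern holds for expression, protein and cell-function comparisons between an infant-heavy category and well controls. The recruitment rule as written allows little or no age overlap, and the plan commits to nothing that would prevent or correct it. This is more than a missing analysis detail, because lost overlap cannot be recovered later.

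The size cannot be stated from the documents. The illustrations show a large loss for an infant-dominated category with equal numbers, a small one for mixed categories, partial recovery with many more controls, and a near-complete barrier when no infant controls exist. These figures rest on the assumed age splits, equal variances and a common effect across bands. The point merits a change to the plan before controls are recruited. It is not evidence that any result would be wrong.

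**What to change.** - Whatever number of well controls is recruited, guide their recruitment by broad age bands (for example under 1, 1-4 and 5-16 years), so that each band holding a substantial share of cases also has controls. State in the plan what share counts as substantial. The bands steer recruitment and are not separate analyses.
- Record age in the clinical dataset, in months for infants.
- Include age in the expression, protein and cell-function models that compare cases with well controls.
- For an age-restricted category, use only controls from the overlapping age bands.

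**Cost.** Infant controls may fill slowly, because only children already having blood taken can be sampled. If a band cannot be filled, report the shortfall and the resulting loss of precision. One shared control group cannot suit every category: moving 50 controls from 10/30/60% to 40/30/30% lowers the older category from 47.6 to 36.3 in the illustration. Equal thirds are a compromise, at 38.2 for both. The change takes no blood from children who would not otherwise be sampled.

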Collaborative work with groups in the CRI will also allow us to monitor influenza strains in circulation in the paediatric population attending St Mary's hospital. Any influenza strains identified in the course of routine virology investigations will be further analysed by [name] group. This surveillance will contribute to maintaining a state of preparedness for an outbreak of pandemic influenza

The CRI has a strong research base in childhood tuberculosis. Recruitment of patients will contribute to the on-going studies in the department which aim to identify serum biomarkers or gene expression profiles that can distinguish patients with TB infection or disease, with a view to improving diagnosis (Newton et al., 2008).

In children with severe bacterial respiratory infection, we are interested in the extent to which lung inflammation and injury is influenced by recent viral infection, as seen in bacterial pneumonias following influenza infection. There is evidence from mice to suggest that after viral infection, there is prolonged down-regulation in the response of the innate immune response to subsequent infections, with the consequence that these infections cause more damage than they would normally (Didierlaurent et al., 2008). Local changes in immune responsiveness may also be important determinants to the outcome of respiratory infection with *Pneumocystis jirovecii* (the cause of pneumocystis pneumonia) in HIV-infected children (Thomas and Limper, 2007). Using BAL or bronchial brushing samples, we would like to examine the immune milieu of children with severe pneumonia caused by different pathogens, using multiplex cytokine analysis and lymphocyte functional characterisation. We will correlate data from bronchial samples with investigations on peripheral blood cells, in

order to determine whether the local immunological changes in the lung are mirrored in peripheral blood.

Principal Objective

We will study a large cohort of children with a broad range of infectious, inflammatory and allergic diseases. We would like to know if we can improve the diagnosis rate in this group of patients, and we will use the latest microbiological approaches to increase our chance of identifying any infection.

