We would like to further our understanding of how children respond to infectious, inflammatory and allergic disease at a genetic, proteomic and cellular level. We will measure these responses using a variety of immunological, molecular biology and proteomic techniques, and correlate the results with the clinical findings. We would therefore hope to develop an increased understanding of disease aetiology. In summary, the principle questions are as follows:

1. What are the bacterial and viral causes of acute illness in children presenting to a UK general hospital, tertiary paediatric infectious disease unit and paediatric intensive care unit?
2. What immunopathogenic mechanisms are involved in severe infection caused by specific bacterial and viral pathogens, and in inflammatory and allergic conditions?

Secondary Objectives

Secondary objectives are considered as sub-headings of the primary objectives

1. What are the bacterial and viral causes of acute illness in children presenting to a UK general hospital, tertiary paediatric infectious disease unit and paediatric intensive care unit?
 - Can we define what proportion of infections are viral and which are bacterial?
 - What is the relationship between viral respiratory infection and bacterial superinfection?
 - What role do infections play in precipitating or extenuating asthma and allergic lung diseases?
 - To what extent does dual infection contribute to increased morbidity?
 - Can the microbiological diagnosis of acute infection in children be improved by application of new diagnostic methods including PCR assays, gene expression profiling, multi-parameter flow cytometry and proteomics?
2. What immunopathogenic mechanisms are involved in severe infection caused by specific bacterial and viral pathogens, and in inflammatory and allergic conditions?
 - To what extent are host inflammatory responses vs. bacterial or viral load important in host injury in infection?
 - What insights do proteomic methods (such as mass spectrometry) and gene expression analysis give into immunopathology of infection?
 - To what extent does heritable genetic variability determine the host response in infection, and does it underlie a predisposition to severe disease?
 - Does heritable genetic variability underlie a predisposition to inflammatory and allergic conditions?
 - To what extent do the immunopathogenic mechanisms identified in animal studies apply in human disease?

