RNA (PAX tubes) will be frozen pending RNA extraction for gene expression analysis.

We will also collect 4ml blood samples for extraction of cells (for instance neutrophils or lymphocytes) or plasma when there is the laboratory capability for immediate processing.

Other samples

Other samples being taken for clinical reason, such as CSF, will be aliquoted for research purposes if there is sufficient. Simple non-invasive tests such as urine collection, throat swab or collection of nasal mucous will be collected in the absence of obvious clinical need if there is fully informed consent.

Where children in the intensive care unit are having bronchoalveolar lavage (BAL) or bronchial brushings for a clinical indication, we will aim to aliquot the sample for research as described.

Processing samples.

Before samples are processed in the laboratory, they will be labelled with a study number, and personal details will be removed. We would not ordinarily expect any further participation in the study after the first time bloods have been taken from the patient.

During their in-patient stay, we will follow the clinical progress of each child in order to document clinical outcome. We may seek consent for additional samples during the patient stay.

Surplus samples.

In the event that clinical samples are taken from a child before there has been an opportunity to enrol them into the study, for instance overnight, we may approach the family to enrol the child. If consent is given, we will endeavour to use any surplus blood or microbiological samples from the clinical diagnostic laboratories.

In this study, it is not necessary that the range of children entering into the study be representative of the clinical range of children with infectious, inflammatory or allergic conditions. Our patient base is in any case distorted by the fact that a disproportionate number of children will be so ill as to need intensive care admission, and the remainder will have been brought to hospital and be ill enough to warrant blood tests. Therefore, we do not expect researcher bias to be a problem. We will keep a clinical dataset for each patient entered into the study so that test results are interpreted in the light of the clinical presentation.

Sample Analysis

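### Does the lack of a rule for setting diagnostic categories independently of the assay undermine signature validation?

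*Combined protocol and SAP*

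**What the plan says.** Three parts of the protocol need a diagnostic category for each child.

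- Secondary Objectives, question 1, asks: "Can the microbiological diagnosis of acute infection in children be improved by application of new diagnostic methods including PCR assays, gene expression profiling", and goes on to name flow cytometry and proteomics.
- Sample Size asks for 30 to 50 children per diagnostic category, with viral against bacterial as the example, and adds: "Confirmatory studies on twice this number are required for validation".
- Statistics and Data Analysis says that "to obtain disease-specific genetic signatures a minimum of 30-50 patients in each group are required, with validation in a larger number". It gives no formal power calculation and places the analysis of complex data with a university biostatistics department.

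On how results are read, Surplus samples says only that a clinical dataset is kept for each child "so that test results are interpreted in the light of the clinical presentation". Just before this, after remarks on the mix of children enrolled, it concludes: "Therefore, we do not expect researcher bias to be a problem".

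On the assays, Principal Objective says that "we will use the latest microbiological approaches to increase our chance of identifying any infection". The section on the Centre for Respiratory Infection says its groups' expertise will be used "both for enhanced diagnostic work on patient samples, and also for scientific lines of enquiry". Under Blood sample collection, "Serum samples will be spun and frozen for proteomic work, such as biomarker characterisation"; RNA tubes are also frozen, while some cells or plasma are processed at once. Processing samples has specimens carry a study number with personal details removed. Data Retention keeps the data for at least 10 years.

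**The concern.** A validation figure can be trusted only if the reference category and the assay are determined separately. If the assay helps to set the category, it is partly compared with itself (incorporation bias). If it is read by someone who knows the category, doubtful readings drift towards agreement (review bias). Neither bias shrinks with sample size, so the larger validation groups that the protocol calls for would not reveal or remove it.

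The protocol states no safeguard against either. It does not say who assigns the category, when, from which data, or without which results. The entry criterion based on clinical judgement covers only a broad infectious, inflammatory or allergic process, so it does not separate bacterial from viral disease. The remark dismissing researcher bias rests on patient mix, which is a different matter. Research PCR looks most exposed, because it is used to find infections and is also listed among the methods under assessment. What would be at stake is a signature or test reported as more accurate than it is.

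**Working it through.** **The plan's own figure.** Validation on double the discovery group gives 2 × 30 = 60 to 2 × 50 = 100 children per category. The 30 to 50 itself cannot be reproduced, because no alpha, power, effect size or variance is given.

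**Does any sentence make an assay set the category?**

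- The clinical-dataset sentence uses clinical data to interpret test results. It does not use test results to assign a category.
- The sentence on researcher bias follows from who is enrolled and is silent on how assays are read.
- Sample Analysis, item 2, suggests that a disease might be marked by its protein pattern. Read naturally, this describes what a signature is; it is not a labelling rule.
- Principal Objective asks whether more children can be given a diagnosis. For that question, letting research PCR add infections is the purpose.

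No passage creates circularity, and none forbids it.

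**How large could it be for signatures?** All inputs here are assumed: true sensitivity Se = 0.80, true specificity Sp = 0.80, bacterial share p = 0.30. The label equals the assay result in a share f of children and the truth in the rest.

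Apparent Se = [p·Se + f(1−p)(1−Sp)] / [p·Se + f(1−p)(1−Sp) + (1−f)p(1−Se)]; apparent Sp follows by symmetry.

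At f = 0.10: (0.240 + 0.014) / (0.254 + 0.054) = 0.254 / 0.308 = 0.825.

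| f | Apparent Se | Apparent Sp |
|---|---|---|
| 0 | 80.0% | 80.0% |
| 0.02 | 80.5% | 80.4% |
| 0.05 | 81.3% | 80.9% |
| 0.10 | 82.5% | 81.8% |

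For review bias, if a share r of wrong calls is re-read to agree, apparent Se = Se + r(1−Se). This gives 81% at r = 0.05 and 82% at r = 0.10.

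**Against sampling error.** The exact 95% interval for 48/60 is 67.7 to 89.2%, and for 80/100 it is 70.8 to 87.3%. These are 21.5 and 16.5 points wide, against shifts of at most 2.5 points.

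**With larger shares.** At p = 0.5 and Se = Sp = 0.80, apparent accuracy is 0.80 + 0.20f: 82% at f = 0.10, 86% at f = 0.30 and 90% at f = 0.50. The last shift, 10 points, matches the approximate 95% half-width at n = 60 (1.96 × √(0.8 × 0.2/60) = 0.101). It would require half of all labels to be copied from the assay.

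**Research PCR.** If every research detection counted as infection, no PCR-positive child could be classed as uninfected, and apparent specificity would be 100% by construction. If only a share g of PCR-only detections counted, the direction could reverse. Assume 30% infected, PCR truly 90% sensitive and 95% specific, and routine tests 60 to 80% sensitive and fully specific. Let N be the number negative on both tests; apparent Sp = N / [N + (1−g) × PCR-only].

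- Routine sensitivity 60%, independent errors, per 1000 children: PCR-only = 108 true + 35 false = 143, and N = 677. At g = 0, 677/820 = 82.6%.
- Routine sensitivity 80%, fully overlapping misses: PCR-only = 30 + 35 = 65, and N = 695. At g = 0, 695/760 = 91.4%.

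Across the scenarios, apparent specificity passes the true 95% at g between about 0.44 and 0.75: it is deflated below that point and inflated above it. The protocol names no PCR specificity as an endpoint.

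**Can separation still be arranged later?** The clinical dataset is retained, serum and RNA are frozen, and samples carry study numbers. Assessors who have not seen the signature result can assign categories from clinical and routine microbiology data when a validation is set up.

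**The case for a change.** The strongest case is that the protocol's own questions depend on a reference category that it never defines, and that a short statement would cost almost nothing. Freezing makes incorporation less likely but does not make the order of work a rule. It does not stop later relabelling, and it does not cover cells processed at once. Nothing says that it covers research PCR. Study numbers hide identity without limiting what the person assigning the category may see. Nor does the protocol say whether research results enter the clinical dataset; if they do, they would have to be withheld from the assessors.

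Most of this stands as a description of what is unwritten. It also stands that such a bias persists however many children are added. What does not stand is the step from silence to likely inflation. The sentence relied on does not describe circular labelling, and for PCR the direction is not even fixed. The claim that independence is lost for good overlooks the retained dataset and frozen samples. Nor is a rule for locking categories free of its own bias, because children left unclassified may be the harder ones. If 20% were unclassified, with accuracy of 60% in them and 85% in the rest (assumed), overall accuracy would be 0.8 × 85 + 0.2 × 60 = 80%. Reporting 85% would overstate it by 5 points, twice the largest signature shift in the table.

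**Conclusion.** No change to the plan follows. The protocol is silent on how categories are assigned for validation, but this is missing operational detail in a broad discovery programme and not a faulty rule. It names no accuracy endpoint, does not say that the confirmatory studies fall under it, and gives the analysis to a biostatistics department that would ordinarily set the reference category apart from the signature. The material for doing so is kept.

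Any inflation is conditional and of unknown size. For signatures it is 0.5 to 2.5 points of sensitivity if 2 to 10% of labels come from the assay, which is small beside the sampling error at 60 to 100 children. That rests on assumed accuracy, prevalence and shares; much larger shares would matter, but nothing in the documents points to them. For research PCR the question asked is added diagnoses, so a specificity calculation does not bear on it. The conclusion would differ if a passage had the signature decide the category, and none does.
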